9. ANALYSIS OF SAFETY

 Edwards	Revision Date: May 7, 2024	Rev	For Use Only by Affiliates of Edwards Lifesciences	Page 19
	Title	A randomized trial of the Hypotension Prediction Index in the cardiac operating room and the intensive care unit		

9.1. Deaths

All deaths that occur for subjects during the study will be presented as the incidence rate and the relationship with the study device and the procedure. Deaths will be summarized for the mITT population by arm.

9.2. Adverse Events

Any adverse event associated with an FDA cleared component will be recorded as a device complaint and reported via the MDR program (21 CFR Part 803).

An adverse device effect (ADE) is defined as an AE related to the use of the medical devices in this trial. This definition includes AEs resulting from insufficient or inadequate instructions for use, deployment, implantation, installation or operation, or any malfunction of the investigation device. It also includes any AE resulting from use error or from intentional misuse of the Trial Device. A serious adverse event (SAE) is defined as an AE that results in any of the following outcomes: death, a life-threatening adverse event, inpatient hospitalization, or prolongation of existing hospitalization, a persistent or significant disability/incapacity, or a congenital anomaly/birth defect. A serious adverse device effect (SADE) is an ADE that has resulted in any of the consequences or characteristics of a SAE.

Unanticipated adverse device effect (UADE) is defined in 21 CFR 812.3(s) as any serious adverse effect on health or safety or any life-threatening problem or death caused by, or associated with, a device, if that effect, problem, or death was not previously identified in nature, severity, or degree of incidence in the investigational plan or application (including supplementary plan or application), or any other unanticipated serious problem associated with a device that relates to the rights, safety, or welfare of subjects. In contrast, an anticipated adverse device effect is an effect which by its nature, incidence, severity, or outcome has been identified in the risk analysis report.

All ADEs, SAEs, SADEs, and UADEs reported for this study will be summarized overall and for events occurring by timepoint (overall, day 0, and days 1-30 days). Only events with onset on or after the procedure date (Day 0) will be summarized in tables. All events that occur before the procedure will be presented in corresponding data listings. These events will be analyzed on the mITT population. Summaries of incidence rates (frequencies and percentages), severity (serious adverse event [SAE] or not), and relationship to procedure and/or device of individual events will be prepared where data is available and presented by arm.

9.3. Imputation for Missing Dates for Safety Events

Algorithms for imputing the missing dates of safety events are given below.

- If the year is unknown, then the date will be imputed using the procedure date
- If the month is unknown, then:
 - If the year matches the year of the procedure date, then impute the month and day using the procedure date
 - Otherwise, assign 'January'

 Edwards	Revision Date: May 7, 2024	Rev	For Use Only by Affiliates of Edwards Lifesciences	Page 20
	Title	A randomized trial of the Hypotension Prediction Index in the cardiac operating room and the intensive care unit		

- If the day is unknown, then:
 - If the month and year match the month and year of the procedure date, then impute the day using the procedure date
 - Otherwise, assign '01'

9.4. Risk Assessments

The safety data will be summarized for all subjects in the safety population (mITT). Safety will be assessed through summarizing adverse events and judging the compliance with study treatment. The frequency and percentage of AEs and SAEs will be reported in summary tables by treatment group. Safety data will not be subjected to any imputation and will be summarized on an observed case basis. Plots showing the incidence of AEs and SAEs and their relative risk (with 95% confidence interval) will also be produced.

10. CHANGES FROM PROTOCOL SPECIFIED ANALYSIS

The protocol calls for an additional analysis of the SOFA score. This score was not collected in the electronic data capture (EDC) system, so it will not be reported.

12. APPENDIX

12.1. Algorithm to Derive Primary Effectiveness Endpoint

The primary effectiveness endpoint of this study is the number of minutes of the intraoperative hypotension instance which is defined as a mean arterial pressure (MAP) below 65 for at least one minute experienced by patients in the cardiac operating room (OR) post-CPB and the cardiovascular intensive care unit (CVICU) up to first 8 hours for patients undergoing cardiac surgery requiring cardiopulmonary bypass, which is calculated with following mathematical procedure.

12.1.1. Detecting the start time and end time of hypotension instance.

The monitoring platform usually samples the cardiac parameters in 20 second intervals. There are rare, sampled measurements that MAPs are exact 65 mmHg for which marks the start time and end time of the hypotension instance. For majority of hypotension instances, the start time point and the end time point with MAP=65 need to be calculated by the consecutive two MAP measurements, one with MAP<65 and one with MAP>65 (intersection point A and B illustrated in Figure 1).

Title

A randomized trial of the Hypotension Prediction Index in the cardiac operating room and the intensive care unit

Illustration Plot: Calculating the Start and End Times of Hypotension Episode

[figure not shown]

Figure 1. An illustration plot of hypotension instance start time and end time calculation

In Figure 1, the duration (the number of minutes) of this hypotension instance is calculated through $\frac{t_B - t_A}{60}$. t_A , t_B is the time corresponding the point A, and B in the plot respectively, which is the intersection point of the line segment of MAP=65 with the line segment from a measurement point with MAP>65 to a point with MAP<65 (instance starting point A), the intersection point of the line segment of MAP=65 with the line segment from a measurement point with MAP<65 to a point with MAP>65 (ending point B). By linear interpolation method or similarity of two right angle triangles, have:

$$t_A = 20 + \overline{C1A} = 20 + 20 \cdot \frac{\overline{C2C1}}{\overline{C2C1} + \overline{D2D1}} = 20 * (1 + \frac{MAP_{C2} - 65}{MAP_{C2} - MAP_{D2}})$$

$$t_B = 100 + \overline{F2B} = 100 + 20 \cdot \frac{\overline{F2F1}}{\overline{F2F1} + \overline{E2E1}} = 100 + 20 \cdot \frac{65 - MAP_{F2}}{MAP_{E1} - MAP_{F2}}$$

Here MAP_{C2} is the MAP value corresponding to the measurement point with time=20 seconds, MAP_{D2} is the MAP value corresponding to the measurement point with time=40 seconds, MAP_{F2} , MAP_{E1} is the MAP value corresponding to the measurement point with time=100 and 120 seconds respectively.

12.1.2. Calculating the duration of hypotension instance

Hypotension duration for this instance is time at point B minus time at point A.

 Edwards	Revision Date: May 7, 2024	Rev	For Use Only by Affiliates of Edwards Lifesciences	Page 23
	Title	A randomized trial of the Hypotension Prediction Index in the cardiac operating room and the intensive care unit		

$$\begin{aligned}
\text{Instance duration} &= (t_B - t_A)/60 = (100 + 20 \cdot \frac{65 - MAP_{F2}}{MAP_{E1} - MAP_{F2}} - 20 - 20 \cdot \frac{MAP_{C2} - 65}{MAP_{C2} - MAP_{D2}})/60 \\
&= (80 + 20 \cdot (\frac{65 - MAP_{F2}}{MAP_{E1} - MAP_{F2}} - \frac{MAP_{C2} - 65}{MAP_{C2} - MAP_{D2}}))/60
\end{aligned}$$

If $\text{Instance duration} \geq 1$ minutes, it is a hypotension instance counted in subject total hypotension duration calculation.

12.1.3. Calculating subject total hypotension duration

$$\text{Total hypotension duration (Subject)} = \sum_{i=1}^n \text{ith hypotension instance duration}$$

Here n is the hypotension instances, if $n = 0$, then this subject's hypotension duration is 0.

12.1.4. Calculating AUC of each hypotension instance, and subject AUC, the additional endpoint

With following trapezoid equation, the AUC (minute*mmHg) for a hypotension instance is calculated.

$$AUC = \sum_{i=1}^m \left(\frac{t_{i+1} - t_i}{60} \right) * \left(65 - \frac{MAP_i + MAP_{i+1}}{2} \right)$$

Here i is the index for consecutive observations, $MAP = 65$ for the start and end points of this hypotension instance, MAP_i, MAP_{i+1} is the MAP value (≤ 65) at $i, i+1$ measurement time respectively.

$$\text{Subject AUC: } AUC = \sum_{j=1}^n AUC_j$$

Here n is the total hypotension instances, if $n=0$ then subject $AUC = 0$.

12.1.5. Calculating Subject TWA, the additional endpoint

With the subject total AUC , TWA is calculated with following equation:

$$TWA = \frac{AUC}{l_m}$$

The unit of TWA is $mmHg$. Here l_m is the length of measurement of study subject in minutes,

$$l_m = \text{last valid EV1000 measure time} - \text{first valid EV1000 measure time}$$

IF $AUC = 0$, then $TWA = 0$ too. Usually l_m is less than surgery duration.

12.2. Algorithm to Derive Compliance

From the protocol, compliance to the study procedure is defined by the following algorithm:

[figure not shown]

Figure 1: HPI Pressure and flow optimization protocol for HPI CARE.

Compliance is defined as

- Any event that lasts less than 2 minutes will be considered an artefact and will be considered a success
- Any event where an intervention occurred from the start time of the HPI alert until 5 minutes after the alert
- Any event where any recommended treatment was ongoing at the time of the start of the alert, with correct defined per the flow diagram
- Any event where any recommended treatment was concluded within 1 minute before the start of an alert. It is assumed that these interventions are in response to a rapidly increasing HPI value

Non-compliance is defined as all other events

- No intervention noted
- No Action, Patient Appears Stable
- Recommendation made (Fluids), provider declined per clinical judgment
- Recommendation made (Inotrope), provider declined per clinical judgment
- Recommendation made (Vasopressor), provider declined per clinical judgment
- If the incorrect treatment was given per the flow diagram

To determine whether the recommendation made matches the treatment given per the flow diagram, we will do as follows.

- Compare the values for SV, SVV, SVR, EaDyn, and dP/dt at the time the alert was triggered with the values recorded 3 minutes prior (now - prior). This will give us the change in each value. For each of these, we will use the table below to determine the recommended treatments:

Edwards

Title

A randomized trial of the Hypotension Prediction Index in the cardiac operating room and the intensive care unit

SV	SVR	EaDyn	dp/dt	SVV		Give Fluids	Give Vasopressor	Give Inotrope
Down	Down	Down	Down	Down		No	Yes	Yes
Down	Down	Down	Down	Neutral		No	Yes	Yes
Down	Down	Down	Down	Up		Yes	Yes	Yes
Down	Down	Down	Neutral	Down		No	Yes	Yes
Down	Down	Down	Neutral	Neutral		No	Yes	Yes
Down	Down	Down	Neutral	Up		Yes	Yes	Yes
Down	Down	Down	Up	Down		No	Yes	Yes
Down	Down	Down	Up	Neutral		No	Yes	Yes
Down	Down	Down	Up	Up		Yes	Yes	Yes
Down	Down	Neutral	Down	Down		No	No	Yes
Down	Down	Neutral	Down	Neutral		No	No	Yes
Down	Down	Neutral	Down	Up		Yes	No	Yes
Down	Down	Neutral	Neutral	Down		No	No	Yes
Down	Down	Neutral	Neutral	Neutral		No	No	Yes
Down	Down	Neutral	Neutral	Up		Yes	No	Yes
Down	Down	Neutral	Up	Down		No	No	Yes
Down	Down	Neutral	Up	Neutral		No	No	Yes
Down	Down	Neutral	Up	Up		Yes	No	Yes
Down	Down	Up	Down	Down		Yes	No	No
Down	Down	Up	Down	Neutral		Yes	No	No
Down	Down	Up	Down	Up		Yes	No	No
Down	Down	Up	Neutral	Down		Yes	No	No
Down	Down	Up	Neutral	Neutral		Yes	No	No
Down	Down	Up	Neutral	Up		Yes	No	No
Down	Down	Up	Up	Down		Yes	No	No
Down	Down	Up	Up	Neutral		Yes	No	No
Down	Down	Up	Up	Up		Yes	No	No
Down	Neutral	Down	Down	Down		Yes	No	Yes
Down	Neutral	Down	Down	Neutral		Yes	No	Yes
Down	Neutral	Down	Down	Up		Yes	No	Yes
Down	Neutral	Down	Neutral	Down		Yes	No	Yes
Down	Neutral	Down	Neutral	Neutral		Yes	No	Yes
Down	Neutral	Down	Neutral	Up		Yes	No	Yes
Down	Neutral	Down	Up	Down		Yes	No	Yes
Down	Neutral	Down	Up	Neutral		Yes	No	Yes
Down	Neutral	Down	Up	Up		Yes	No	Yes
Down	Neutral	Neutral	Down	Down		Yes	No	Yes
Down	Neutral	Neutral	Down	Neutral		Yes	No	Yes

Title

A randomized trial of the Hypotension Prediction Index in the cardiac operating room and the intensive care unit

SV	SVR	EaDyn	dp/dt	SVV		Give Fluids	Give Vasopressor	Give Inotrope
Down	Neutral	Neutral	Down	Up		Yes	No	Yes
Down	Neutral	Neutral	Neutral	Down		Yes	No	Yes
Down	Neutral	Neutral	Neutral	Neutral		Yes	No	Yes
Down	Neutral	Neutral	Neutral	Up		Yes	No	Yes
Down	Neutral	Neutral	Up	Down		Yes	No	Yes
Down	Neutral	Neutral	Up	Neutral		Yes	No	Yes
Down	Neutral	Neutral	Up	Up		Yes	No	Yes
Down	Neutral	Up	Down	Down		Yes	No	No
Down	Neutral	Up	Down	Neutral		Yes	No	No
Down	Neutral	Up	Down	Up		Yes	No	No
Down	Neutral	Up	Neutral	Down		Yes	No	No
Down	Neutral	Up	Neutral	Neutral		Yes	No	No
Down	Neutral	Up	Neutral	Up		Yes	No	No
Down	Neutral	Up	Up	Down		Yes	No	No
Down	Neutral	Up	Up	Neutral		Yes	No	No
Down	Neutral	Up	Up	Up		Yes	No	No
Down	Up	Down	Down	Down		Yes	No	Yes
Down	Up	Down	Down	Neutral		Yes	No	Yes
Down	Up	Down	Down	Up		Yes	No	Yes
Down	Up	Down	Neutral	Down		Yes	No	Yes
Down	Up	Down	Neutral	Neutral		Yes	No	Yes
Down	Up	Down	Neutral	Up		Yes	No	Yes
Down	Up	Down	Up	Down		Yes	No	Yes
Down	Up	Down	Up	Neutral		Yes	No	Yes
Down	Up	Down	Up	Up		Yes	No	Yes
Down	Up	Neutral	Down	Down		Yes	No	Yes
Down	Up	Neutral	Down	Neutral		Yes	No	Yes
Down	Up	Neutral	Down	Up		Yes	No	Yes
Down	Up	Neutral	Neutral	Down		Yes	No	Yes
Down	Up	Neutral	Neutral	Neutral		Yes	No	Yes
Down	Up	Neutral	Neutral	Up		Yes	No	Yes
Down	Up	Neutral	Up	Down		Yes	No	Yes
Down	Up	Neutral	Up	Neutral		Yes	No	Yes
Down	Up	Neutral	Up	Up		Yes	No	Yes
Down	Up	Up	Down	Down		Yes	No	Yes
Down	Up	Up	Down	Neutral		Yes	No	Yes
Down	Up	Up	Down	Up		Yes	No	Yes
Down	Up	Up	Neutral	Down		Yes	No	Yes

Title

A randomized trial of the Hypotension Prediction Index in the cardiac operating room and the intensive care unit

SV	SVR	EaDyn	dp/dt	SVV		Give Fluids	Give Vasopressor	Give Inotrope
Down	Up	Up	Neutral	Neutral		Yes	No	Yes
Down	Up	Up	Neutral	Up		Yes	No	Yes
Down	Up	Up	Up	Down		Yes	No	Yes
Down	Up	Up	Up	Neutral		Yes	No	Yes
Down	Up	Up	Up	Up		Yes	No	Yes
Neutral	Down	Down	Down	Down		No	Yes	Yes
Neutral	Down	Down	Down	Neutral		No	Yes	Yes
Neutral	Down	Down	Down	Up		No	Yes	Yes
Neutral	Down	Down	Neutral	Down		No	Yes	No
Neutral	Down	Down	Neutral	Neutral		No	Yes	No
Neutral	Down	Down	Neutral	Up		No	Yes	No
Neutral	Down	Down	Up	Down		No	Yes	No
Neutral	Down	Down	Up	Neutral		No	Yes	No
Neutral	Down	Down	Up	Up		No	Yes	No
Neutral	Down	Neutral	Down	Down		No	Yes	Yes
Neutral	Down	Neutral	Down	Neutral		No	Yes	Yes
Neutral	Down	Neutral	Down	Up		No	Yes	Yes
Neutral	Down	Neutral	Neutral	Down		No	Yes	No
Neutral	Down	Neutral	Neutral	Neutral		No	Yes	No
Neutral	Down	Neutral	Neutral	Up		No	Yes	No
Neutral	Down	Neutral	Up	Down		No	Yes	No
Neutral	Down	Neutral	Up	Neutral		No	Yes	No
Neutral	Down	Neutral	Up	Up		No	Yes	No
Neutral	Down	Up	Down	Down		No	Yes	No
Neutral	Down	Up	Down	Neutral		No	Yes	No
Neutral	Down	Up	Down	Up		Yes	Yes	No
Neutral	Down	Up	Neutral	Down		No	Yes	No
Neutral	Down	Up	Neutral	Neutral		No	Yes	No
Neutral	Down	Up	Neutral	Up		Yes	Yes	No
Neutral	Down	Up	Up	Down		No	Yes	No
Neutral	Down	Up	Up	Neutral		No	Yes	No
Neutral	Down	Up	Up	Up		Yes	Yes	No
Neutral	Neutral	Down	Down	Down		No	Yes	Yes
Neutral	Neutral	Down	Down	Neutral		No	Yes	Yes
Neutral	Neutral	Down	Down	Up		Yes	Yes	Yes
Neutral	Neutral	Down	Neutral	Down		No	Yes	No
Neutral	Neutral	Down	Neutral	Neutral		No	Yes	No
Neutral	Neutral	Down	Neutral	Up		Yes	Yes	No

Edwards

Title

A randomized trial of the Hypotension Prediction Index in the cardiac operating room and the intensive care unit

SV	SVR	EaDyn	dp/dt	SVV		Give Fluids	Give Vasopressor	Give Inotrope
Neutral	Neutral	Down	Up	Down		No	Yes	No
Neutral	Neutral	Down	Up	Neutral		No	Yes	No
Neutral	Neutral	Down	Up	Up		Yes	Yes	No
Neutral	Neutral	Neutral	Down	Down		No	No	Yes
Neutral	Neutral	Neutral	Down	Neutral		No	No	Yes
Neutral	Neutral	Neutral	Down	Up		Yes	No	Yes
Neutral	Neutral	Neutral	Neutral	Down		No	No	No
Neutral	Neutral	Neutral	Neutral	Neutral		No	No	No
Neutral	Neutral	Neutral	Neutral	Up		Yes	No	No
Neutral	Neutral	Neutral	Up	Down		No	No	No
Neutral	Neutral	Neutral	Up	Neutral		No	No	No
Neutral	Neutral	Neutral	Up	Up		Yes	No	No
Neutral	Neutral	Up	Down	Down		Yes	No	No
Neutral	Neutral	Up	Down	Neutral		Yes	No	No
Neutral	Neutral	Up	Down	Up		Yes	No	No
Neutral	Neutral	Up	Neutral	Down		Yes	No	No
Neutral	Neutral	Up	Neutral	Neutral		Yes	No	No
Neutral	Neutral	Up	Neutral	Up		Yes	No	No
Neutral	Neutral	Up	Up	Down		Yes	No	No
Neutral	Neutral	Up	Up	Neutral		Yes	No	No
Neutral	Neutral	Up	Up	Up		Yes	No	No
Neutral	Up	Down	Down	Down		No	Yes	Yes
Neutral	Up	Down	Down	Neutral		No	Yes	Yes
Neutral	Up	Down	Down	Up		Yes	Yes	Yes
Neutral	Up	Down	Neutral	Down		No	Yes	Yes
Neutral	Up	Down	Neutral	Neutral		No	Yes	Yes
Neutral	Up	Down	Neutral	Up		Yes	Yes	Yes
Neutral	Up	Down	Up	Down		No	Yes	Yes
Neutral	Up	Down	Up	Neutral		No	Yes	Yes
Neutral	Up	Down	Up	Up		Yes	Yes	Yes
Neutral	Up	Neutral	Down	Down		No	No	Yes
Neutral	Up	Neutral	Down	Neutral		No	No	Yes
Neutral	Up	Neutral	Down	Up		Yes	No	Yes
Neutral	Up	Neutral	Neutral	Down		No	No	Yes
Neutral	Up	Neutral	Neutral	Neutral		No	No	Yes
Neutral	Up	Neutral	Neutral	Up		Yes	No	Yes
Neutral	Up	Neutral	Up	Down		No	No	Yes
Neutral	Up	Neutral	Up	Neutral		No	No	Yes

SV	SVR	EaDyn	dp/dt	SVV		Give Fluids	Give Vasopressor	Give Inotrope
Neutral	Up	Neutral	Up	Up		Yes	No	Yes
Neutral	Up	Up	Down	Down		Yes	No	Yes
Neutral	Up	Up	Down	Neutral		Yes	No	Yes
Neutral	Up	Up	Down	Up		Yes	No	Yes
Neutral	Up	Up	Neutral	Down		Yes	No	No
Neutral	Up	Up	Neutral	Neutral		Yes	No	No
Neutral	Up	Up	Neutral	Up		Yes	No	No
Neutral	Up	Up	Up	Down		Yes	No	No
Neutral	Up	Up	Up	Neutral		Yes	No	No
Neutral	Up	Up	Up	Up		Yes	No	No
Up	Down	Down	Down	Down		No	Yes	Yes
Up	Down	Down	Down	Neutral		No	Yes	Yes
Up	Down	Down	Down	Up		No	Yes	Yes
Up	Down	Down	Neutral	Down		No	Yes	No
Up	Down	Down	Neutral	Neutral		No	Yes	No
Up	Down	Down	Neutral	Up		No	Yes	No
Up	Down	Down	Up	Down		No	Yes	No
Up	Down	Down	Up	Neutral		No	Yes	No
Up	Down	Down	Up	Up		No	Yes	No
Up	Down	Neutral	Down	Down		No	Yes	Yes
Up	Down	Neutral	Down	Neutral		No	Yes	Yes
Up	Down	Neutral	Down	Up		No	Yes	Yes
Up	Down	Neutral	Neutral	Down		No	Yes	No
Up	Down	Neutral	Neutral	Neutral		No	Yes	No
Up	Down	Neutral	Neutral	Up		No	Yes	No
Up	Down	Neutral	Up	Down		No	Yes	No
Up	Down	Neutral	Up	Neutral		No	Yes	No
Up	Down	Neutral	Up	Up		No	Yes	No
Up	Down	Up	Down	Down		No	Yes	No
Up	Down	Up	Down	Neutral		No	Yes	No
Up	Down	Up	Down	Up		Yes	Yes	No
Up	Down	Up	Neutral	Down		No	Yes	No
Up	Down	Up	Neutral	Neutral		No	Yes	No
Up	Down	Up	Neutral	Up		Yes	Yes	No
Up	Down	Up	Up	Down		No	Yes	No
Up	Down	Up	Up	Neutral		No	Yes	No
Up	Down	Up	Up	Up		Yes	Yes	No
Up	Neutral	Down	Down	Down		No	Yes	Yes

Edwards

Title

A randomized trial of the Hypotension Prediction Index in the cardiac operating room and the intensive care unit

SV	SVR	EaDyn	dp/dt	SVV		Give Fluids	Give Vasopressor	Give Inotrope
Up	Neutral	Down	Down	Neutral		No	Yes	Yes
Up	Neutral	Down	Down	Up		Yes	Yes	Yes
Up	Neutral	Down	Neutral	Down		No	Yes	No
Up	Neutral	Down	Neutral	Neutral		No	Yes	No
Up	Neutral	Down	Neutral	Up		Yes	Yes	No
Up	Neutral	Down	Up	Down		No	Yes	No
Up	Neutral	Down	Up	Neutral		No	Yes	No
Up	Neutral	Down	Up	Up		Yes	Yes	No
Up	Neutral	Neutral	Down	Down		No	No	Yes
Up	Neutral	Neutral	Down	Neutral		No	No	Yes
Up	Neutral	Neutral	Down	Up		Yes	No	Yes
Up	Neutral	Neutral	Neutral	Down		No	No	No
Up	Neutral	Neutral	Neutral	Neutral		No	No	No
Up	Neutral	Neutral	Neutral	Up		Yes	No	No
Up	Neutral	Neutral	Up	Down		No	No	No
Up	Neutral	Neutral	Up	Neutral		No	No	No
Up	Neutral	Neutral	Up	Up		Yes	No	No
Up	Neutral	Up	Down	Down		Yes	No	No
Up	Neutral	Up	Down	Neutral		Yes	No	No
Up	Neutral	Up	Down	Up		Yes	No	No
Up	Neutral	Up	Neutral	Down		Yes	No	No
Up	Neutral	Up	Neutral	Neutral		Yes	No	No
Up	Neutral	Up	Neutral	Up		Yes	No	No
Up	Neutral	Up	Up	Down		Yes	No	No
Up	Neutral	Up	Up	Neutral		Yes	No	No
Up	Neutral	Up	Up	Up		Yes	No	No
Up	Up	Down	Down	Down		No	Yes	Yes
Up	Up	Down	Down	Neutral		No	Yes	Yes
Up	Up	Down	Down	Up		Yes	Yes	Yes
Up	Up	Down	Neutral	Down		No	Yes	Yes
Up	Up	Down	Neutral	Neutral		No	Yes	Yes
Up	Up	Down	Neutral	Up		Yes	Yes	Yes
Up	Up	Down	Up	Down		No	Yes	Yes
Up	Up	Down	Up	Neutral		No	Yes	Yes
Up	Up	Down	Up	Up		Yes	Yes	Yes
Up	Up	Neutral	Down	Down		No	No	Yes
Up	Up	Neutral	Down	Neutral		No	No	Yes
Up	Up	Neutral	Down	Up		Yes	No	Yes

Edwards

Title

A randomized trial of the Hypotension Prediction Index in the cardiac operating room and the intensive care unit

SV	SVR	EaDyn	dp/dt	SVV		Give Fluids	Give Vasopressor	Give Inotrope
Up	Up	Neutral	Neutral	Down		No	No	Yes
Up	Up	Neutral	Neutral	Neutral		No	No	Yes
Up	Up	Neutral	Neutral	Up		Yes	No	Yes
Up	Up	Neutral	Up	Down		No	No	Yes
Up	Up	Neutral	Up	Neutral		No	No	Yes
Up	Up	Neutral	Up	Up		Yes	No	Yes
Up	Up	Up	Down	Down		Yes	No	Yes
Up	Up	Up	Down	Neutral		Yes	No	Yes
Up	Up	Up	Down	Up		Yes	No	Yes
Up	Up	Up	Neutral	Down		Yes	No	No
Up	Up	Up	Neutral	Neutral		Yes	No	No
Up	Up	Up	Neutral	Up		Yes	No	No
Up	Up	Up	Up	Down		Yes	No	No
Up	Up	Up	Up	Neutral		Yes	No	No
Up	Up	Up	Up	Up		Yes	No	No

 Edwards	Revision Date: May 7, 2024		Rev	For Use Only by Affiliates of Edwards Lifesciences	Page 32
	Title	A randomized trial of the Hypotension Prediction Index in the cardiac operating room and the intensive care unit			

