All the other statistical methodology used in sensitivity analysis, safety analysis, and exploratory analysis will be detailed in the SAP.

Note: In this study, the sample size is not big enough to ignore the approximate property with Z score test, especially in the interim analysis.

Planned Interim Analyses

To monitor the effectiveness and safety of HPI software on hypotension management in cardiac surgery and ICU, one interim analysis is planned and will be conducted at the time that half of the enrolled study subjects complete surgery and the hemodynamic measurements are downloaded from the monitoring platform.

To compensate for the early look at the data during the interim analysis, using the Pocock methodology, for this study design, 11% extra study subjects will be enrolled. Considering drop-out through ICF withdrawal, subjects lost to follow-up, and roll-in subjects for training, another 10% attrition is added for subject enrollment; the final sample size is 175 subjects per group.

Secondary Endpoints

The following secondary endpoints will be analyzed per the SAP:

- TWA of MAP < 65 mmHg in the OR Period (T1)
- TWA of MAP < 65 mmHg in the CVICU Period (T2)
- TWA of MAP < 65 mmHg in the CVICU Period, pre extubation (T3)
- TWA of MAP < 65 mmHg in the CVICU Period, post extubation (T4)
- Mean duration in minutes of MAP < 65 mmHg in the time periods of T1, T2, T3 and T4
- Mean duration in minutes of MAP < 60 mmHg in the time periods of T1, T2, T3 and T4
- Mean duration in minutes of MAP < 55 mmHg in the time periods of T1, T2, T3 and T4
- Mean duration in minutes of MAP < 50 mmHg in the time periods of T1, T2, T3 and T4

Clinical endpoints:

- Acute kidney injury (AKI)⁷, as defined by the modified KDIGO criteria, stages 1, 2 and 3.
- Neurocognitive deficit, as evaluated by the MMSE, CAM-ICU 7, and bCAM assessments.
- Periprocedural Myocardial injury, measured with high-sensitivity Troponin I and as defined a threshold of 70 times the upper reference limit⁶. or >1400 pg/ml

THIS DOCUMENT CONTAINS CONFIDENTIAL AND PROPRIETARY INFORMATION OF EDWARDS LIFESCIENCES, LLC. IT MAY NOT BE REPRODUCED OR DISCLOSED WITHOUT PRIOR WRITTEN PERMISSION FROM EDWARDS LIFESCIENCES, LLC.

Edwards Lifesciences, Edwards, the stylized E logo, HemoSphere, Acumen IQ, Swan Ganz and ForeSight Elite are trademarks of Edwards Lifesciences Corporation.

Additional Evaluations

The following additional evaluations will be included and are considered exploratory:

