- Subgroup analysis of primary and secondary endpoints by age stratification
- Subgroup analysis of primary and secondary endpoints by gender
- Subgroup analysis of primary and secondary endpoints by race
- Protocol adherence to HPI alert, as defined by >50% HPI alerts with documented intervention per the suggested treatment algorithm within a 5 minute timeframe
- Difference in time spent in hypertension defined as TWA of MAP>110, >120 and >130 mmHg post-cardiopulmonary bypass CPB) through the first 8-hour ICU period as compared with the control group.
- In-hospital mortality rate
- Incidence of cerebral desaturations defined as total time below 10% relative to baseline NIRS values.
- Percent of monitoring time with CO or CI within 10% relative to pre-induction baseline
- ICU Length of Stay
- Hospital Length of Stay
- Time to extubation
- SOFA scores
- New onset atrial fibrillation detected prior to ICU discharge

THIS DOCUMENT CONTAINS CONFIDENTIAL AND PROPRIETARY INFORMATION OF EDWARDS LIFESCIENCES, LLC. IT MAY NOT BE REPRODUCED OR DISCLOSED WITHOUT PRIOR WRITTEN PERMISSION FROM EDWARDS LIFESCIENCES, LLC.

Edwards Lifesciences, Edwards, the stylized E logo, HemoSphere, Acumen IQ, Swan Ganz and ForeSight Elite are trademarks of Edwards Lifesciences Corporation.

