8.6. Exploratory Analyses

The following exploratory analyses will be performed. These analyses will be presented for the FAS population.

- Protocol adherence to HPI alert, as defined by >50% HPI alerts with documented intervention per the suggested treatment algorithm within a 5-minute timeframe

 Edwards	Revision Date: May 7, 2024	Rev	For Use Only by Affiliates of Edwards Lifesciences	Page 18
	Title	A randomized trial of the Hypotension Prediction Index in the cardiac operating room and the intensive care unit		

For each subject, it is likely that there will be several decisions necessary. Each decision will be made separately, and the overall rate of compliance will be calculated.

A full definition of the compliance algorithm, can be found in section 12.2.

- Difference in time spent in hypertension defined as TWA of MAP>110, >120 and >130 mmHg post-cardiopulmonary bypass CPB) through the first 8-hour ICU period as compared with the control group. The time spent in hypertension will be calculated in a similar manner to the primary endpoint. The only difference will be that we are looking for the amount of time above the hypertension thresholds instead of below it. The average time will be calculated by arm and the difference will also be presented.
- In-hospital mortality rate
The mortality rate will be calculated as a simple proportion for each arm and for the difference between the two arms.
 - Incidence of cerebral desaturations defined as total time below 10% relative to baseline NIRS values. For each subject, the baseline NIRS value will be established at The time below 10%
- Percent of monitoring time with CO or CI within 10% relative to pre-induction baseline
The baseline CO and CI will be calculated pre-induction. The percent of the monitoring time within 10% of the baseline value will be calculated and presented by and for the difference between the arms.
- Hospital Length of Stay (days)
The hospital length of stay will be calculated starting with the procedure time until the subject is discharged. LoS will be calculated and presented by and for the difference between the arms.
- ICU Length of Stay (hours)
- Time to extubation (hours)
The time to extubation will be calculated as the amount of time from intubation until extubation. The average time will be presented by arm and the difference will also be presented.
- New onset atrial fibrillation, detected prior to ICU discharge

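### SAP 12.2 does not measure the adherence endpoint it is meant to derive: alerts under 2 minutes score as successes, and the scoring of non-matching and unrecommended treatment is not settled

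*Combined protocol and SAP*

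**What the plan says.** The protocol (section 7, Additional Evaluations) defines the endpoint as "Protocol adherence to HPI alert, as defined by >50% HPI alerts with documented intervention per the suggested treatment algorithm within a 5 minute timeframe", and SAP 8.6 repeats it. The protocol introduces the list that contains it with "The following additional evaluations will be included and are considered exploratory".

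SAP 12.2 turns this into a scoring rule for each alert. Four kinds of event are compliant:

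1. "Any event that lasts less than 2 minutes will be considered an artefact and will be considered a success"
2. "Any event where an intervention occurred from the start time of the HPI alert until 5 minutes after the alert"
3. "Any event where any recommended treatment was ongoing at the time of the start of the alert, with correct defined per the flow diagram"
4. A recommended treatment that ended no more than 1 minute before the alert began.

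Everything else is non-compliant. The items listed there include an alert with no intervention noted, "No Action, Patient Appears Stable", and "If the incorrect treatment was given per the flow diagram".

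A table then maps the direction of change in five parameters to the treatments recommended. SAP section 10, on changes from the protocol, mentions only the SOFA score. SAP section 1 says that the SAP prevails in a conflict.

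**The concern.** An alert judged to be an artefact gave nobody anything to adhere to, yet it enters both the numerator and the denominator as a success. The endpoint definition contains no such credit. The second compliant item drops the word recommended, which the third and fourth items keep, so it is unclear whether a treatment must match the table. Some table rows recommend nothing, and the text does not say how an alert in such a row is to be scored.

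Adherence is the plan's defined measure of whether the HPI-guided strategy was delivered, and it carries a 50% cut-off. It will be used to interpret the primary result, whether null or positive. SAP 9.4 also brings compliance with treatment into the safety assessment, though without citing 12.2. As written, two programmers could report different rates from the same data, and a rate below 50% among assessable alerts could be reported as above it.

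**Working it through.** The documents give no adherence result, so there is no stated figure to reproduce. I read an event in 12.2 as an HPI alert.

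**Short alerts.** Let s be the share of alerts under 2 minutes, c the adherence among alerts of 2 minutes or more, and d the share of short alerts that did have a qualifying documented intervention. None of these is given, so all values are assumptions.

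Reported rate = s + (1 − s)c. For c = 40%:

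| s | Reported rate | Short alerts removed | Difference, s(1 − c) |
|---|---|---|---|
| 10% | 0.10 + 0.90 × 0.40 = 46% | 40% | 6 points |
| 20% | 0.20 + 0.80 × 0.40 = 52% | 40% | 12 points |
| 30% | 0.30 + 0.70 × 0.40 = 58% | 40% | 18 points |

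A value of c below 50% is lifted past the cut-off when s > (0.5 − c)/(1 − c):

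- c = 45%: 0.05/0.55 = 9.1%
- c = 40%: 0.10/0.60 = 16.7%
- c = 30%: 0.20/0.70 = 28.6%

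If short alerts are instead kept and credited only when treated, the rate is sd + (1 − s)c and the inflation is s(1 − d). That is zero if every short alert was treated and at most s if none was. At s = 20% and c = 40%, this rate lies between 32% (d = 0) and 52% (d = 1), against 52% reported. On either comparison the rule never lowers the rate.

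**Non-matching treatment.** Take an alert of 4 minutes with a treatment at minute 3 that the table does not recommend. The second compliant item accepts it, because an intervention occurred in the window. The last non-compliant item rejects it, because the treatment was incorrect. No precedence is stated. If non-compliance is purely the residual class, the second item wins and the incorrect-treatment item has almost nothing left to catch. If the incorrect-treatment item wins, the second item must be read as requiring a match.

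**Rows without a recommendation.** Five parameters with three levels give 3^5 = 243 rows, all present and distinct. The tally is:

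- fluids and inotrope 62
- fluids 52
- vasopressor 44
- vasopressor and inotrope 34
- inotrope 22
- all three 11
- fluids and vasopressor 10
- none 8

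The eight have SV Neutral or Up, SVR Neutral, EaDyn Neutral, dP/dt Neutral or Up, and SVV Down or Neutral: 2 × 1 × 1 × 2 × 2 = 8, and 8/243 = 3.3%. For alerts of 2 minutes or more in these rows:

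| Action | If a match is required | If any intervention counts |
|---|---|---|
| None | Non-compliant | Non-compliant |
| Any treatment in the window | Non-compliant | Compliant |

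If u is the share of longer alerts falling in these rows, the strict reading caps their adherence at 1 − u: 90% at u = 10% and 80% at u = 20%. It would be 96.7% if all 243 patterns were equally likely, which nothing in the documents supports.

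**The case against.** **A match was clearly intended.** Non-compliance is a residual class, the text after the lists explains how to check treatment against the table, and the endpoint refers to the suggested algorithm. On this view the second item is a wording slip. I agree that a match is the likelier intention, but the SAP does not say so, and adopting that reading leaves the eight rows with no way to comply.

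**A short alert may be short because it was treated promptly.** This stands. It would be tempting to treat c as the true adherence and to assume that nobody acted during short alerts. The documents do not support that: the rule applies with or without an intervention, so inflation against the endpoint's own definition ranges from zero to s. Removing short alerts is one reasonable convention, and it would drop some that were properly treated. Hence the separate count proposed below.

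**The second and third defects rest on different readings.** Correct. The double classification arises if the second item is read literally; the impossibility of complying in the eight rows arises if it requires a match. They do not operate together. Under the literal reading the eight rows have a different fault: following the table fails and departing from it passes. In all cases an alert under 2 minutes is a success.

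**The flow diagram is not shown.** It may define Neutral or deal with a pattern that recommends nothing. This limits the third part of the point.

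**The stakes are modest.** The endpoint is exploratory with no hypothesis test, and fluid and vasoactive drug records give other evidence of what was delivered. Both stand.

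**Conclusion.** The point holds as one of definition. The short-alert rule departs from the endpoint, can only raise the reported rate, and is not listed as a change. With c = 40%, it adds 6 to 18 points compared with removing short alerts at s = 10% to 30%. Compared with crediting only treated short alerts, it adds between nothing and s. Both rest on assumed values, and the formula applies whether the 50% cut-off is meant per subject or over pooled alerts, which the SAP leaves unclear. The other two defects leave the rate not uniquely defined.

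A reader might infer that the adherence result will be wrong, or that the strategy was not delivered. Neither follows. No result exists, and under the strict reading the eight rows pull the rate down while the short-alert rule pulls it up, so the net effect depends on unknown shares. A reader might also take 3.3% as the share of alerts affected; it is a share of table patterns, and how often they occur depends on a cut-off for Neutral that the text does not give. The primary test, alpha and sample size are untouched.

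**What to change.** In SAP 12.2:

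- Remove alerts under 2 minutes from numerator and denominator. Report separately how many there were and how many had a documented intervention.
- Reword the second compliant item so that the intervention in the 5-minute window must be one that the table recommends for that pattern.
- Treat the eight no-recommendation patterns as not evaluable for adherence and report how many alerts fell in them. If the flow diagram does not define Neutral, state the cut-off.
- Report separately the share counted as compliant only because a treatment was already ongoing.

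In SAP section 10, list the departure from the protocol's definition.

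The cost is SAP wording and a small change to the compliance program, with no new data. The adherence figure may become less favourable and its denominator smaller. No view is taken on which treatment the table should recommend.
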